- (1) Adult men and woman with a diagnosis of PD.
- (2) Patients who are candidates for bilateral STN DBS placement surgery and who will receive this treatment as part of their routine care.
- (3) Willingness to undergo temporary changes in STN DBS generator settings.

PROTOCOL TITLE: Safety and feasibility of using low frequency deep brain stimulation of the subthalamic nucleus to improve cognitive performance in patients with Parkinson's disease

(4) Patients who have a caregiver who is willing to answer psychological screening questions on behalf of the patient.

Exclusion criteria:

- (1) Patients less than 18 years of age.
- (2) Patients who are not candidates for bilateral STN DBS placement surgery.
- (3) Adults unable to consent
- (4) Pregnant woman
- (5) Prisoners
- (6) Patients who score over 20 on the BDI indicating moderate depression

7) Number of Subjects

The target sample size is 22 subjects. The study design is a phase 1 safety and feasibility study. While results may show a trend towards efficacy, we will not be able to power the study toward efficacy. Two of these subjects will be used to evaluate the ease of use of the computerized cognitive test, but will not participate in any other study procedures and data will not become part of the study record. All subjects are to be enrolled locally at UC Davis medical center.

8) Recruitment Methods

a) Study-Wide:

NA

b) Local:

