As part of our routine clinical practice at UC Davis, all patients that undergo STN DBS surgery are discussed in detail at the multidisciplinary Deep Brain Stimulation Case Conference, which includes representatives from Neurology, Psychiatry, Speech/Cognitive Therapy, and Neurosurgery. If patients are a candidate for the operation and score less than 20 on the baseline routine BDI, they are candidates for this study. Therefore, at the pre-operative visit with the patient they will be informed that, independent of their eligibility for DBS surgery, they may be eligible for a study investigating DBS frequency on cognitive performance in Parkinson's disease. If patients are interested in participating, they will be offered the opportunity to meet with a member of the study personnel that can provide them additional, detailed information regarding the study. The study personnel will be different from the treating neurosurgeon so that potential participants do not feel pressured to participate in the study. Consent forms will be provided with written information about the study goals, risks, and benefits.

Patients that plan to undergo STN DBS surgery at Sutter Medical Center and Kaiser Permanente in Sacramento may also be able to participate in this study. 'Dear Doctor' letters will be distributed to the Sutter and Kaiser DBS groups. Patients will be provided with a contact number to call if they are interested in learning more about the study. The

PROTOCOL TITLE: Safety and feasibility of using low frequency deep brain stimulation of the subthalamic nucleus to improve cognitive performance in patients with Parkinson's disease

study will briefly be described on the phone. Patients interested in participating will be invited to UC Davis to meet with study personnel to review the study goals, risks and benefits in more detail. Consent forms will be provided at this visit and baseline cognitive testing will be performed if the patient decides to participate.

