The dates of contact and written consent or refusal will be recorded. Participants will be advised that they have the right to say “Refuse to answer” to any questions that they find uncomfortable. They will be assured that participation is on a voluntary basis and they reserve the right to withdraw participation in the study at any point of time, and that declining to participate in the study will not have any effect on their medical care. Participants will be notified that with their consent, the research team will share any data collected from the screening and the study with their doctors at the end of their participation in the study.

An advertisement will be posted in the newspaper to recruit patients for the study. This advertisement will give a brief description of the study and instruct interested individuals to contact study personnel at the number provided to learn more about the study.

c) HIPAA:

As described in Question 8b above, the main eligibility criterion for this study is eligibility for STN DBS surgery. Therefore, the DBS Case Conference team will review individuals' medical records during evaluation for DBS surgery, per routine clinical practice at our institution. If the patient is a candidate for STN DBS and scores less than 20 on the BDI on routine screening tests, then a review of medical records may be performed to determine eligibility based on the inclusion/exclusion criteria above. Since medical records will be accessed prior to signing the consent form or HIPAA authorization, we request a waiver of HIPAA for recruitment purposes only. The use or disclosure of the PHI involves no more than a minimal risk to the privacy of individuals. All identifiers will be password-protected and access to data files will be given only to IRB- approved research personnel as listed in the research personnel list. Identifiers will be destroyed at the earliest opportunity consistent with the conduct of the research, unless there is a health or research justification for retaining the identifiers or such retention is otherwise required by law.

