a) Neuropsychiatric tests. We will perform the BDI and NPI at baseline, at the first experimental session, once by telephone call after 24 hours of LFS, and a fourth time at the final experimental session. The score of the BDI will be compared across sessions and a score that rises above 20 will be considered positive for the development of moderate depression. The NPI assesses frequency, change in severity, and caregiver distress over 12 neuropsychiatric domains and we will look for caregiver reports of significant change across these domains.

b) Motor tests. The Unified Parkinson's Disease Rating Scale (UPDRS) will be performed prior to patient's surgery as part of the patient's routine care. We will repeat the scale at the final experimental session to assess changes in motor symptoms after sustained LFS.

c) Changes in cognitive function will also be assessed as described below.

2. Feasibility. Improvement in cognitive function will be measured by three cognitive tests: the Stroop test, the N-Back test, and the verbal fluency test. We will measure reaction time and error rates and look for significant changes across stimulator frequencies. The results from 20 patients will help us determine if a large-scale study of effectiveness is warranted and feasible.

Describe any primary or secondary safety endpoints.

See above.

PROTOCOL TITLE: Safety and feasibility of using low frequency deep brain stimulation of the subthalamic nucleus to improve cognitive performance in patients with Parkinson's disease

12) Procedures Involved

a) Describe and explain the study design.

The study design is a safety and feasibility study. We aim to identify 20 PD patients who will receive bilateral STN DBS as part of their standard care. We plan to measure the safety of LFS in the STN as measured through psychological, cognitive, and motor scales, and compare cognitive performance with low and high frequency STN DBS. We propose that LFS in the theta range will not negatively affect psychiatric symptoms or alter motor symptoms, and will improve performance on tests of executive functioning.

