Upon informed consent and enrollment, information regarding participants’ age, gender, medications, medical history, surgical history, disease duration and imaging (magnetic resonance imaging, computed tomography) will be collected. As part of the standard assessment prior to DBS electrode placement, all patients undergo evaluation with the Unified Parkinson’s Disease Rating Scale (UPDRS), Beck depression inventory (BDI) (Beck et al 1961), IQ testing, and a battery of neurocognitive tests. These tests are routinely repeated about 6 months to 1 year after DBS placement as part of patients’ routine care. These tests will not be a direct part of the study but may be utilized as part of the patient’s history.

As part of our experimental design, we will include a baseline experimental session prior to the patient’s planned surgery that will consist of approximately 30 minutes of cognitive testing and baseline screening for neuropsychiatric symptoms using the BDI and NPI (Cummings et al 1994). Cognitive testing will consist of computerized and non-computerized tests. The NPI requires that a caregiver answer questions about the mental state and behaviors of the patient. The caregiver will be informed of the study at the pre-op visit if the patient consents and will be asked if they are willing to participate in the study procedure.

After patients’ treatment team has performed their DBS surgeries, there will be two on-site experimental testing sessions with frequency manipulation and a telephone psychological screening session. The first will occur 22-24 days following the DBS lead placement surgery. During the session, each patient will repeat baseline cognitive testing

PROTOCOL TITLE: Safety and feasibility of using low frequency deep brain stimulation of the subthalamic nucleus to improve cognitive performance in patients with Parkinson's disease

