without stimulation and will complete the BDI. Informers will complete the NPI. Subsequently, the stimulators will be turned on, and each patient will repeat cognitive testing under gamma frequency (~130 Hz) and theta frequency stimulation (~5 Hz). The order of stimulation will be randomized. Stimulation will occur for 5 minutes prior to and continuously throughout each task. Amplitude and pulse width will be set to 3 V and 120 microseconds accordingly (Laxton & Lozano 2013) or as tolerated by the patient, and will remain constant across sessions. We will wait 20 minutes between testing conditions to elicit about 75% of DBS effects (Temperli et al 2003). At the end of the experimental testing session, the stimulator will be turned off or set to LFS in preparation for the second experimental session.

The second on-site experimental testing session will assess the effects of continuous theta stimulation on cognitive function. Patients will repeat cognitive testing after 48 hours of continuous theta stimulation. This second on-site testing session will occur 3-5 days following the first experimental session. Two days prior to the testing session, patients' stimulators will be turned on to the theta frequency stimulation setting and patients will return home and engage in normal activities. After 48 hours they will return to the clinic and repeat cognitive testing with continuous theta frequency stimulation. The UPDRS, NPI, and BDI will also be performed at this time. At the end of the session, their stimulators will be turned off.

We will screen for psychological changes by telephone once during the 2 day stimulation period. The patient will complete the BDI and a relative or caregiver will complete the NPI over the phone.

The structure of the experimental sessions is shown in Figure 2 and Figure 3.

[figure not shown]

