to rely on connections between the basal ganglia and the prefrontal cortex (Dadgar et al 2013, Jaywant et al 2014). Furthermore, DBS has been shown in some studies to impair phonemic verbal fluency, which may or may not recover over time (Ehlen et al 2014, Wojtecki et al 2006, Wu et al 2014). These specific letters were chosen based on the frequency of English language words that begin with the letters (Borkowski et al 1967.)

Total testing time will be approximately 30 minutes per stimulation condition with 20 minutes between conditions, resulting in a total time of approximately 30 minutes for the baseline cognitive testing, 2 hours for the first experimental session and 30 minutes for the second experimental session. Additional time will be needed for setup and explanation of the task directions. Finally, 20 minutes of psychological screening will be performed at the baseline session, over the phone between experimental sessions 1 and 2, and following cognitive testing during experimental session 2.

Baseline Testing: 30 min cognitive testing, 20 minute psychological screening (Total Time: approximately 50 min)

Experimental Session 1: 20 minutes psychological screening, 2 hours cognitive testing (Total Time: approximately 2h 20 min)

Phone call between experimental session 1 and 2: 20 minutes psychological screening

Experimental Session 2: 30 min cognitive testing, 20 minute psychological screening, 20 min motor screening (Total Time: approximately 70 minutes)

b) Humanitarian Use Device (HUD)

NA

13) Data and Specimen Banking

No data or specimens will be retained longer than required by law or hospital policy.

14) Data Management and Confidentiality

The target sample size is 22 subjects. The study design is a safety and feasibility phase 1 study. While results may show a trend towards efficacy, we will not be able to power the study toward efficacy.

Safety Data Analysis:

To examine possible effects on motor symptoms, we will screen for changes in the motor section of the UPDRS score after sustained LFS. After each patient is tested, we will calculate individual changes in UPDRS scoring. After the entire patient population is tested, we will use T-tests to determine if there is a significant change in the overall rating scale.

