We will also examine changes in psychological symptoms. For each individual patient, we will measure the BDI and NPI at baseline, at the first experimental session, by phone call after 24 h LFS, and at the final experimental session. For the BDI, we will consider any score greater or equal to 20 as evidence of moderate depression and will terminate the study for any individual that shows evidence of depression. At the group level, we will calculate

PROTOCOL TITLE: Safety and feasibility of using low frequency deep brain stimulation of the subthalamic nucleus to improve cognitive performance in patients with Parkinson's disease

the percentage of people that develop depression. For the NPI, we will calculate the total score. At the individual level we will look for the development of new symptoms in the 12 subsections. At the group level we will perform an ANOVA to look for significant changes across the 3 time points.

Cognitive Data Analysis:

The cognitive data analysis will examine the effect of theta frequency stimulation on cognitive task performance. Analyses for the Stroop task will include the examination of response time and error rates across stimulator settings. Two (trial type: congruent vs incongruent) by three (Setting: low, high, no stimulation) ANOVAs will be performed for both reaction time and accuracy. Post conflict and post error reaction time adjustments will also be examined across stimulator settings. For the N-back test, ANOVAs will also be performed to assess the effects of complexity (1,2-back) and stimulation frequency (none, high, low) on error rates. For the verbal fluency test, the average number of words generated across stimulation conditions and the change in word number on low and high frequency stimulation settings will be compared. Analyses will be performed using MATLAB and STATA.

Describe any procedures that will be used for quality control of collected data.

a.) Study-Wide:

NA

b.) Local

Describe the local procedures for maintenance of confidentiality.

This research is partly funded by a donation from the Chevo Foundation. The Chevo Foundation will not have access to any of the study documents including the data.

Data files to be stored include group assignment, background information, any head scans if performed, and results from neurocognitive and motor tests.

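### The BDI cut-off conflicts at a score of exactly 20, and the psychiatric safety analyses name no reference visit, so a case arising after surgery but before stimulation may be reported under low frequency stimulation

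*Combined protocol and SAP*

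**What the plan says.** **Cut-off.** The BDI threshold appears in five sections or subsections, with two different boundaries.

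- Section 6, exclusion criterion 6: "Patients who score over 20 on the BDI indicating moderate depression".
- Section 8b, candidates: "score less than 20 on the baseline routine BDI". Section 8c repeats this: "scores less than 20 on the BDI on routine screening tests".
- Section 11, endpoint 1a: "a score that rises above 20 will be considered positive for the development of moderate depression".
- Section 14, Safety Data Analysis: "we will consider any score greater or equal to 20 as evidence of moderate depression and will terminate the study for any individual" with such evidence.
- Section 15, Safety Data Analysis: conversion to moderate depression is a score of 20 or higher.

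**Visits.** Sections 11, 14 and 15 give four BDI and NPI assessments: before surgery (baseline), at the first experimental session (E1), by telephone after 24 hours of LFS, and at the final session (E2). On E1, section 12 says "The first will occur 22-24 days following the DBS lead placement surgery". Cognitive testing at that visit is first done "without stimulation and will complete the BDI. Informers will complete the NPI. Subsequently, the stimulators will be turned on".

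**Analyses.** At group level, section 14 reports the percentage who develop depression and runs an NPI ANOVA over three time points that it does not name. Section 15 reports the percentage who convert, and runs BDI and NPI ANOVAs over time. No section states a reference visit or a contrast. The testing-time summary in section 12 says "psychological screening will be performed at the baseline session, over the phone between experimental sessions 1 and 2, and following cognitive testing during experimental session", meaning the final one. This leaves out E1, but the session list directly below it includes screening at E1.

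**The concern.** Monitoring the psychological consequences of LFS is part of aim 1, and the results are meant to inform a larger trial. The depression percentage is the headline psychiatric figure. As the text stands, it can change for two reasons unrelated to what LFS does.

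First, a score of exactly 20 is or is not an event depending on which section the analyst follows. A patient with a baseline of 20 could also enrol under section 6 and meet the section 14 termination rule at once.

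Second, the words used for the outcome (rises, develops, converts) imply incidence, but the starting point is not given. Between baseline and E1 the patient has had lead and pulse generator surgery and no stimulation. A new score of 20 or more at E1 is a post-surgical finding, and counting it under LFS overstates LFS harm.

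The same ambiguity affects the ANOVAs. If the pre-surgical baseline is one of the time points, a significant time effect does not show whether scores moved with surgery or with LFS.

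**Working it through.** The plan gives no power, alpha or precision figure for this point, so there is none to reproduce. The number of patients in the stimulation study is 22 - 2 = 20 (section 7, after removing the two who only try out the computer test).

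**Step 1. Apply each rule to scores around 20.**

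| Rule | 19 | 20 | 21 |
|---|---|---|---|
| Section 6, excluded if over 20 | eligible | eligible | excluded |
| Section 8b/8c, candidate if under 20 | candidate | not a candidate | not a candidate |
| Section 11, event if above 20 | no | no | yes |
| Section 14, event and termination if 20 or more | no | yes | yes |
| Section 15, event if 20 or more | no | yes | yes |

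The conflict is confined to exactly 20. It affects eligibility and event status, and it sets eligibility against the stopping rule. If one patient scores exactly 20 after LFS starts and no other patient has an event, the result is 0/20 = 0% (exact 95% CI 0-16.8%) under section 11 and 1/20 = 5.0% (0.1-24.9%) under sections 14 and 15.

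**Step 2. Follow a patient who first reaches 20 at E1.** The E1 BDI is taken 22-24 days after lead surgery with stimulation off. Section 14 lists the four assessments and then applies its rule to any score, so E1 is covered. Reading the outcome as a change from the visit called baseline gives the same answer, because that visit is before surgery. Section 14 also ends this patient's participation, so the patient would not go on to LFS.

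**Step 3. Size of one such case, with no other events.** Exact (Clopper-Pearson) 95% limits for x of n are the 2.5% point of Beta(x, n-x+1) and the 97.5% point of Beta(x+1, n-x). For x = 0 the lower limit is 0 and the upper limit is 1 - 0.025^(1/n).

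- Counted: 1/20 = 5.0% (0.1-24.9%).
- LFS-emergent events only, with the patient out of numerator and denominator: 0/19 = 0%, upper limit 1 - 0.025^(1/19) = 17.6%. This assumes that the other 19 all start sustained LFS.

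**Step 4. How likely is at least one such case?** The documents give no rate. For an assumed rate p, the chance among 20 patients is 1 - (1-p)^20: 33% at p = 2%, 64% at 5% and 88% at 10%. These are illustrations only.

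**Step 5. Time points.** Four assessments are collected and three are analysed for the NPI. If the three are E1, phone and E2, the analysis compares scores under LFS with a post-surgical, pre-stimulation score. Any set that includes the pre-surgical baseline spans surgery as well. The set in the section 12 summary sentence (baseline, phone, E2) would also drop the only assessment that separates the two.

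**The case against.** - **No sentence says that an E1 case counts.** This stands. A reader might infer that the plan instructs the analyst to count it. The documents do not say so; they leave the reference undefined. Counting is the plain reading of section 14 and also follows from a pre-surgical reference, but it remains a reading.
- **The case would be visible.** An E1 case would be a dated withdrawal before stimulation, and any error overstates harm. Both are true. However, the planned group summary is a percentage, and nothing asks for cases to be listed by visit.
- **The cut-off conflict is narrow.** It concerns one integer score. Both analysis sections agree on 20 or more, and the numeric termination rule appears only once. Section 8 ties its under-20 rule to the routine BDI on the UC Davis pathway; for Sutter, Kaiser and newspaper recruits only section 6 clearly applies. The conflict is small but explicit.
- **Three time points may mean E1, phone and E2.** That reading is permissible and would be the right analysis. It also means that changing three to four would not help by itself, because it would put the pre-surgical baseline into the test for certain.
- **The section 12 summary sentence concerns visit length.** This is fair. The session list and sections 11, 14 and 15 all place an assessment at E1, so the omission there is clerical.
- **This is an unpowered phase 1 study.** This also stands, and it argues for a simple fix. It does not justify leaving the reference visit unstated.

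**Conclusion.** The point holds as a modest should-fix. The conflict at a BDI of exactly 20 is certain from the text, as is the mismatch between four collected and three unnamed analysed time points. That a pre-LFS case would enter the depression percentage is the plain reading, but it is not stated outright. Each such case moves the percentage by 1/20 = 5 percentage points; how often one would occur is unknown.

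Two stronger readings are tempting and are not supported. A reader might infer that the ANOVAs would hide a real LFS effect or produce significant results at some calculable rate. Hiding an effect would need E1 to be the omitted visit and a surgical change that roughly cancels the LFS change. Any rate would need BDI and NPI distributions, a surgical shift and an allowance for the section 14 termination rule, and the documents give none of the numerical inputs. What can be said is that an ANOVA including the pre-surgical baseline mixes surgical change with LFS change.

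A reader might also infer that individual patients are unprotected. Section 15 has the study team review data after each visit and call, and that safeguard is unaffected.

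**What to change.** 1. Use a BDI of 20 or more as the single cut-off for exclusion, event and termination in sections 6, 8, 11, 14 and 15, for every recruitment route.
2. Define an LFS-emergent event as a BDI below 20 at E1 and 20 or more at the phone call or E2, among patients who start sustained LFS. Report cases at E1 separately as post-surgical.
3. Make phone minus E1 and E2 minus E1 the main comparisons for both BDI and NPI. If an ANOVA is kept, name its three time points as E1, phone and E2. Report the pre-surgical baseline descriptively.
4. State that attribution to LFS stays limited even so, because there is no concurrent control and brief high frequency stimulation is given at E1.

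The cost is wording and analysis code. All four assessments are already collected, so no visit, test or patient is added.

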Safety data will include performance on psychological screening tests, cognitive tests, and motor tests. Efficacy data will include performance on cognitive tests. All data will be reviewed by a safety committee as described above. If any patient develops motor effects that are uncomfortable, the study will be halted for that particular subject. Furthermore, if the patient develops worsening psychological effects as measured through psychological screening tools, the study will be halted and the patient will be referred for appropriate care through the departments of Psychiatry and Neurology at UC Davis.

Safety information will be collected at study visits and with a telephone call. It will be saved in the database established for this study.

Safety data for motor effects will be collected prior to the patient's surgery and at the final study visit. Psychological data will be collected prior to DBS placement, at the first study visit, by phone call during the sustained frequency stimulation period, and at the final clinic visit.

The principal investigator and study members will review the data after each clinic visit and telephone contact with the patient. A safety committee will review the data after the first 4 patients, 8 patients, 12 patients, and 20 patients. The committee will include the PI, [name] in addition to [name], [name], and [name]. [name] is a neurologist, co-director of the DBS group, and has participated in multiple clinical trials involving the Parkinson's disease population. [name] is an expert in neurocognitive assessment in Parkinson's disease and has experience in identifying study related neurocognitive effects in clinical trials in dementia.

Data will be analyzed and evaluated in cohorts of 4 patients through the first 12 patients to determine whether subjects remain safe. This means we will evaluate the safety data from the first 4 patients before proceeding with subsequent subjects. We will evaluate data again after a total of 8 patients, 12 patients, and 20 patients.

PROTOCOL TITLE: Safety and feasibility of using low frequency deep brain stimulation of the subthalamic nucleus to improve cognitive performance in patients with Parkinson's disease

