Safety Data Analysis: To examine possible effects on motor symptoms, we will screen for significant changes in the motor section of the UPDRS score after sustained LFS. After each patient is tested, we will calculate individual changes in UPDRS scoring. After the entire patient population is tested, we will use a T-test to determine if there is a significant change the motor section.

We will also examine changes in psychological symptoms using the BDI and NPI. We will examine percentage of people who convert to moderate depression as indicated by a BDI score 20 or higher. We will also look for significant changes in the BDI and NPI across time using ANOVAs.

Changes in cognition will also be analyzed by looking at reaction time and error rates on different cognitive tests as described previously.

- Any conditions that trigger an immediate suspension of the research.

None.

16) Withdrawal of Subjects

Describe anticipated circumstances under which subjects will be withdrawn from the research without their consent.

Patients unable to perform cognitive tests due to effort or altered mental status.

Patients who experience any change in psychological symptoms that is concerning to the patient, caregiver, or test administrator as assessed through psychological screening tools.

Describe any procedures for orderly termination.

The patient is not undergoing any additional procedures, except for stimulation and cognitive testing.

Describe procedures that will be followed when subjects withdraw from the research, including partial withdrawal from procedures with continued data collection.

Patients' data will be recorded, unless specifically asked to be withdrawn

Patients will continue to be followed for medical management

17) Risks to Subjects

Physical Risk:

- There is minimal to no physical risk. Once the patient's stimulation is turned off, the patient's pre-stimulation symptoms will likely return (Temperli et al 2003).
- There is a small chance that changes in affective symptoms including dysphoria, depression, mania, or psychosis may occur (Smeding et al 2006, Strutt et al 2012). Patients will be carefully screened using standardized assessment tools.
- All cognitive and memory tests are designed to be minimally difficult and pose minimal

PROTOCOL TITLE: Safety and feasibility of using low frequency deep brain stimulation of the subthalamic nucleus to improve cognitive performance in patients with Parkinson's disease

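### The individual psychological safety analysis names only new NPI symptoms and a BDI of 20 or more, so worsening that the endpoint and monitoring text covers has no defined place in the reported result

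*Combined protocol and SAP*

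**What the plan says.** **Endpoint (section 11, item 1a).** For the NPI, the stated aim is: "we will look for caregiver reports of significant change across these domains". What makes a change significant is not defined. The instrument is described as recording how often symptoms occur, how their severity changes, and how much they distress the caregiver, in 12 domains. On the BDI: "The score of the BDI will be compared across sessions and a score that rises above 20 will be considered positive".

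**Analysis (section 14, Safety Data Analysis).** On the BDI: "For the BDI, we will consider any score greater or equal to 20 as evidence of moderate depression". At group level the percentage of patients who develop depression is calculated. On the NPI: "At the individual level we will look for the development of new symptoms in the 12 subsections". The group analysis of the NPI is an ANOVA over three time points, although the same paragraph lists four assessments: baseline, first experimental session (E1), telephone call, and final session (E2).

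**Monitoring (section 15).** "if the patient develops worsening psychological effects as measured through psychological screening tools, the study will be halted", with referral. Data are reviewed after each visit and call, safety information is saved in the study database, and a safety committee meets after 4, 8, 12 and 20 patients. The Safety Data Analysis text there says: "We will examine percentage of people who convert to moderate depression as indicated by a BDI score 20 or higher". It adds ANOVAs of the BDI and NPI over time.

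**Withdrawal (section 16).** A change in psychological symptoms that worries the patient, the caregiver or the tester is a ground for withdrawal.

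**The concern.** Aim 1 is the safety of low frequency stimulation (LFS), including its psychological consequences. The endpoint and monitoring sections treat worsening as the thing to detect. The analysis section, which determines what is reported, states two narrower individual criteria: a symptom that was absent and appears, and a BDI at or above a fixed level. A patient whose mild irritability or apathy becomes severe under LFS meets neither.

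No reference visit is given for a new symptom. Measured against the pre-operative baseline, a symptom that follows surgery would count as new. Measured against E1, where the BDI and NPI are taken before stimulation is switched on, it would not. Attribution to LFS depends on that choice.

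The motor analysis in section 14 shows the gap, because individual changes in UPDRS score are to be calculated after each patient. No matching individual change is planned for the BDI or NPI. In a study of 20 treated patients, one or two markedly worse patients may be the whole safety signal.

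**Working it through.** The plan states no figure on this point, so there is none to reproduce. The check has three parts.

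**1. Which individual changes are counted?**

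| Change from E1 to an LFS assessment | Section 14 rule | Endpoint and monitoring text |
|---|---|---|
| NPI symptom absent, then present | Counted | Covered |
| NPI symptom mild, then severe | Not counted | Covered (section 11 change; section 15 worsening) |
| BDI 5 to 19 (19 − 5 = +14) | Not counted | Covered by comparison across sessions |
| BDI 10 to 19 (19 − 10 = +9) | Not counted | Covered by comparison across sessions |
| BDI 19 to 20 (+1) | Counted | Not positive under section 11, which requires a score above 20 |

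**2. Can the group test stand in for an individual criterion?**

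Inputs: n = 20 treated patients (section 7: 22 enrolled, less 2 who only try out the computer test). Two-sided 0.05 is my assumption, since no level is stated. Suppose k patients worsen by the same amount d and the other n − k do not change at all. There is then no background variation to hide the signal.

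- Paired contrast: t = √[k(n − 1)/(n − k)]
- One-way repeated-measures ANOVA: F = k(n − 1)/(n − k), with 2 and 38 degrees of freedom for three time points, or 3 and 57 for four

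The amount d cancels, so a larger rise does not help. Unequal rises among the k patients give a smaller t. The plan specifies the ANOVA; the paired t is shown as the simplest before-and-after contrast.

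| k | t | p (t) | F | p (3 time points) | p (4 time points) |
|---|---|---|---|---|---|
| 1 | √(19/19) = 1.00 | 0.33 | 19/19 = 1.00 | 0.38 | 0.40 |
| 2 | √(38/18) = 1.45 | 0.16 | 38/18 = 2.11 | 0.14 | 0.11 |
| 3 | √(57/17) = 1.83 | 0.083 | 57/17 = 3.35 | 0.046 | 0.025 |
| 4 | √(76/16) = 2.18 | 0.042 | 76/16 = 4.75 | 0.014 | 0.005 |

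One or two worsened patients do not reach 0.05 even in this ideal setting. Three do so in the ANOVA, provided nobody else changes.

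**3. Which time points enter the ANOVA?**

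Sections 11 and 14 list four BDI and NPI assessments, and section 14 analyses the NPI over three. The documents do not say which is left out. In section 12a, the paragraph on total testing time names three screening occasions and omits E1, while the itemised schedule directly below it includes E1. If E1 is the one left out, the group test also loses its only post-operative reference without stimulation.

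**The case against.** The strongest reply is that worsening is not ignored. Section 11 covers change in severity across NPI domains and compares the BDI across sessions. Section 14 introduces its psychological analysis as one of changes and does not say that new symptoms are all it will look at. Sections 15 and 16 halt or withdraw patients who worsen, data are reviewed after every contact and saved, and with 20 patients the individual records are open to inspection.

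Most of this stands. A reader might infer that harm is counted only as a new symptom or a BDI of 20, and that other worsening goes unrecorded. The documents do not support that reading: the scores are collected, reviewed, acted on and stored.

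The reply does not supply the missing definition. The monitoring rules give neither a size of change nor a reference visit, and no planned analysis counts the patients halted or withdrawn. Worsening first found at E2 is found when stimulation is turned off and participation ends anyway, so the halting rule need leave no trace of it.

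A second reply is fair. Counting any rise from E1 will list chance fluctuation as well. The documents give no retest error for either scale, so its frequency cannot be worked out from them. For the same reason, nothing here should be taken to mean that BDI scores reaching 20 would mostly be noise. This is a reason to show changes by size and not as a yes-or-no event.

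**Conclusion.** The point holds as an inconsistency between sections. Endpoint and monitoring text cover worsening, but the individual analysis in section 14 neither defines nor tabulates it and names no reference visit. The reported individual result could show no psychological events although a patient's existing symptom became severe, or a BDI rose by as much as 14 from a score of 5.

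The group analysis cannot make this good for one or two patients in 20: the best case gives ANOVA p-values of 0.38 to 0.40 for one patient and 0.11 to 0.14 for two. Those figures assume equal rises, no change in anyone else, and a 0.05 level that the plan does not state. The textual finding needs none of these assumptions.

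The change should be made, but existing safeguards limit what is at stake. The weakness is in what is reported, and the documents do not show that patients go unmonitored.

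**What to change.** In section 14, and in the matching text of section 15:

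- For each patient and each of the 12 NPI domains, report new symptoms and also the increase in domain score from the unstimulated E1 assessment, at the telephone call and at E2, shown by size. State which of the collected NPI items form the domain score.
- Report each patient's BDI change from E1 beside the 20-point status.
- Report the number of patients halted or withdrawn for psychological worsening.
- Reconcile the BDI wording: above 20 in section 11, 20 or higher in sections 14 and 15. Section 14 also ties the end of an individual's participation to this score, so those responsible for clinical decisions must settle it. No value is proposed here.
- Reconcile the four NPI assessments with the three time points in the ANOVA, and say which assessments enter.

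The stopping and withdrawal rules are otherwise untouched. The cost is analysis wording and one per-patient table from scores already collected. The drawback is that more increases will be listed, some of them retest noise. Showing their size lets a reader tell a one-point drift from a marked deterioration.
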